## **GLOSSARY**

**BCTs** Behaviour Change Techniques

Co-I Co-investigator

DCE Discrete Choice Experiment

FFIT Football Fans in Training research study

HIC Health Informatics Centre, University of Dundee

IP Intellectual Property

Ipsos MORI A UK Market Research Company (https://www.ipsos-mori.com/)

MHF Men's Health Forum

NIHR National Institute of Health Research

NICE National Institute for Health and Care Excellence

PA Physical Activity

PPI Public and Patient Involvement in research

QOF Quality and Outcomes Framework for GP Practices

QALYs Quality-adjusted Life Year

RCT Randomised Controlled Trial

Researchers Employees of the University of Stirling to conduct the research

SMS Short Message Service (commonly known as text message)

**SPCRN** Scottish Primary Care Research Network

TCTU Tayside Clinical Trials Unit

TSC Trial Steering Committee

## 1a. LAY SUMMARY

In 2014, 24% of UK men were obese. However men rarely participate in weight loss programmes. This study looks at whether two interventions which show promise can help obese men lose weight and keep it off.

INTERVENTION 1: Sending (and receiving) text messages to a mobile phone. These will be written as though they come from other men who are also losing weight and include 'how to do it' diet and physical activity tips, combined with friendly humour and support.

INTERVENTION 2: The same texts plus promising men money (up to £400) at the start contingent on weight loss achievement. The money will vary over a year according to whether weight targets are met (5% of body weight lost at 3 months, 10% at 6 months and 10% at 12 months after the start of the study). This is called an endowment incentive and is based on research showing that modest payment helps people change their diet and physical activity. At the 3, 6 and 12 month weighing appointments, men will have the option of continuing with the original weight loss targets of 5%, 10% and 10% or setting lower targets of 5% of body weight at 6 months and 5% at 12 months. This is to maintain motivation and hope for men who do not meet the more ambitious weight loss targets.

WE WANT TO FIND OUT if the texts work better with incentives than alone. Both interventions are delivered from a computer and have potential to reach large numbers, including men who don't use health services. This work is done together with obese men and a charity for men to help us find the best ways to deliver the interventions to as many men as possible, including men in difficult life situations.

## THE STUDY HAS TWO PARTS:

PHASE 1. Is in progress and is setting up the feasibility trial. Phase 1 has approval from the University of Stirling Research Ethics Committee.

PHASE 2. We will study whether it is acceptable and possible to randomise obese men (like tossing a coin) to three groups: texts only; texts and incentive; or to a 'control group' who wait a year and then get the texts for 3 months. We will assess the feasibility of recruiting 105 obese men from two regions of Scotland. Half of the men will get an invitation letter from their GP. The other half will be approached in the community, given information about the study and invited to take part. Men can take part if their trouser waist is 40 inches and more or their Body Mass Index is 30 or higher. We want to find out how long it takes to find 105 obese men who want to take part, how many come back to suitable venues at 3, 6 and 12 months to get weighed and answer questions about their quality of life, lifestyle and motivation. We will try to include men from all walks of life, so we will ask questions at the start like their age, address, who they live with, or if they have any illnesses like diabetes. At the end we will ask men about their experiences and men from the control group will receive texts for 3 months if they wish. Control group texts will be developed based on the feedback and qualitative interview data received from the men in the two intervention groups at 3 months. In order to improve the acceptability of the texts to more men, these texts will be a different style from the original narrative texts. Drop-outs from the control group at 12 months will be replaced through recruiting further men until we have a sample of at least 30 men receiving the alternative texts. We will interview approximately 18-30 men in more detail about their experiences of weight loss and of being in the study. We will follow up all men from the alternative text group for 3 months, seek their feedback on the texts and interview 10-16 men in more depth about their experience. A PhD student will find out if it is possible to follow up the men for another year, and ask them questions on whether it is acceptable and possible to link the study findings to their health records.

Protocol, Game of Stones. V3, 14/02/2018

THE STUDY WILL TELL US if our approach is acceptable, possible to deliver and if it could help men to lose weight. If it is, then we will do a larger study.

#### 1b SCIENTIFIC SUMMARY

**IMPORTANCE:** In 2014, 24% of UK men were obese and this prevalence is increasing. Systematic reviews suggest that far fewer men than women engage in formal weight loss programmes, but if they do they are less likely to drop out.

#### MAIN RESEARCH QUESTIONS:

- 1. Is a narrative SMS intervention with embedded behaviour change techniques (BCTs) and endowment incentives acceptable and feasible to deliver in a RCT?
- 2. How can intervention components and delivery processes be optimised to increase reach, engagement and follow up of obese men?
- 3. Are progression criteria met for a full RCT for one or both interventions?
- 4. What are the likely recruitment and attrition rates?
- 5. What would be the sample size for a full trial?

**AIM:** To co-produce with PPI, an acceptable and feasible RCT design with wide reach to test a narrative SMS intervention with embedded BCTs, with and without an endowment incentive, compared to waiting list. This will inform a future pragmatic, full-scale effectiveness and cost-effectiveness trial

**DESIGN:** A two phase feasibility study.

Phase 1 i) finalise the design of a narrative SMS intervention with embedded BCTs for men using qualitative research with representatives of the target population and PPI, and ii) develop an endowment incentive drawing on insights from behavioural economics, existing evidence and men's preferences for delivery based on survey/DCE evidence. Systematic review evidence, theory and learning from recent UK behaviour change trials were combined with an iterative mixed methods approach to refine the interventions through PPI and user testing.

Phase 2 is a 12 month feasibility RCT with 3 arms: SMS only; SMS and incentive; usual practice with waiting list for SMS intervention. Iterative mixed method data collection and analysis will help to refine the intervention parameters, design and processes in preparation for a potential full pragmatic effectiveness and cost-effectiveness

**RCT SETTING:** 2 communities in Scotland with disadvantaged areas; differing in employment, ethnic groups, urban and rural access

**POPULATION:** Obese adult men with BMI 30 or over and/or waist measurement 40 inches (102cm) or over. Recruitment through community venues (50%) and GP obesity registers (50%). Phase 1: a survey/DCE (n=1045 obese men); qualitative interviews/focus groups with 20-30 men, diverse PPI and a stakeholder workshop to finalise the intervention. Phase 2: 105 men randomised to three groups (n=35 each) and approximately 18-30 qualitative interviews

**INTERVENTIONS:** 1.Narrative SMS with embedded BCTs; 2.The same SMS plus endowment incentives

**CONTROL:** Waiting list for 12 months followed by an offer of alternative SMS intervention for 3 months based on feedback from intervention participants

**ALL GROUPS:** A pedometer for PA monitoring

**PRIMARY OUTCOMES:** Acceptability and feasibility of recruitment, retention, intervention components, time points for verifying weight with feasibility of assessor blinding, identifying core outcomes that are acceptable and matter for obese men

**SECONDARY OUTCOMES:** Differential recruitment, engagement with narrative SMS and incentive components and attrition by socio-economic status and setting. Quality of motivation (intrinsic and extrinsic), satisfaction with weight loss, qualitative experiences, risk of incentive gaming. Optimising retention, engagement, and follow-up using feedback received from men who have participated in the intervention arms of the feasibility trial. Meeting progression criteria, calculating the sample size and securing intervention funds for a full trial. Feasibility of follow up for a year after the intervention and data linkage to routinely collected health outcomes.

**LIKELY FULL RCT PRIMARY OUTCOME:** Weight loss at 1 year. SECONDARY: % weight loss, waist circumference, QALYs, costs

**IMPACT:** A novel theory based intervention ready for a full RCT, with broad reach and with central delivery at scale.

## 2. BACKGROUND

In the UK 24% of men are obese, with higher prevalence in those from deprived backgrounds. Obesity conveys an increased risk of serious health conditions and is a major public health priority. This proposal is in response to a commissioned call which NIHR has identified as a research priority topic. Our novel narrative SMS and endowment incentive feasibility study fits the research recommendations in recent NIHR reviews and NICE recommendations to investigate i) "components, or combinations of components, that support weight loss or the prevention of weight regain", ii) "the effect of new technologies" and iii) "specific behaviour change techniques" (BCTs). This study is informed by two NIHR funded trials (three studies) of narrative SMS for alcohol problems (including in obese men) which are successfully recruiting hard to reach men and showing high engagement.

## 2.1. EXISTING RESEARCH

Despite a growing problem of overweight and obesity men are an underserved population in current evidence-based weight management programmes. Most interventions are designed for mixed sex or female only populations despite evidence that many men desire different interventions to women. Consequently limited evidence exists on the most effective strategies to recruit and retain men in weight management programmes. Innovative means of delivering male obesity interventions are needed, particularly for hard-to-reach groups. Although some evidence of effective lifestyle interventions for obesity exists, little research to date has systematically consulted men on how to optimise engagement and make interventions user-friendly. Rigorous feasibility studies and piloting with service user input at all stages is recommended. The cost-effectiveness of interventions for men is limited.

The maintenance of initial weight loss is generally poor. Evidence suggests that ongoing and long-term support for weight loss maintenance is required, yet few weight management programmes are designed with maintenance in mind. Evidence points to the need for male-specific highly engaging interventions that target weight maintenance. There are good theoretical reasons and growing empirical evidence to suggest that theory-based interventions delivered by SMS, and financial incentives may both engage men and result in weight loss maintenance. However, no trials have examined SMS in obese men with or without incentives.

## 2.2. RATIONALE FOR CURRENT STUDY

There is accumulating evidence that some weight management services need to be different for men (than for women) and that PPI is needed in their design. Recent reports  recommend testing systematic, multiple interventions delivered at scale and experimentation where risk is low. Meaningful engagement of men reluctant to join existing services, particularly from disadvantaged backgrounds is important to address health inequalities.

Throughout this protocol, we use the term 'diet' however dieting terms are not popular with men and in the interventions we will refer to changing and reducing food and drink (including alcohol) intake. Although lifestyle interventions with reducing diets and increasing PA are clinically effective, only 10-20% of participants are men and the type of diet does not affect long term weight loss. The most effective interventions for men include specific behaviour change techniques (BCTs) to support translating diet and PA change targets into performance. Examples of BCTs from effective interventions are action planning (e.g. specifying what to change, when and where), self-monitoring (e.g. keeping a food and stepcount diary) and relapse prevention (e.g. planning how to respond to a lapse following initial change). If men can be engaged through an intervention that embeds evidence-based BCTs then there is potential for significant health gains. We will assess the feasibility of two novel and promising interventions for weight management in obese men to inform the design of a future full trial.

**Impact:** Given financial pressures within the NHS, acceptable and effective low cost obesity interventions will be highly sought after by NHS managers in the future. Innovative, efficient and scalable interventions, with broad reach and high engagement, are required to support obese men's weight management. This is the first study to test a narrative SMS intervention, with and without financial incentives. The study will provide new evidence on whether financial incentives are needed to increase uptake, intervention engagement and adherence, and the impact on health inequalities. If found to be effective, centralised delivery of automated SMS with or without incentives, will facilitate implementation at scale. The interventions and the optimisation of forms of delivery have potential for generalisability to other populations or health behaviours.

## Building on existing work and pilot studies

There is strong empirical support from NIHR studies for engagement of men with the narrative SMS for alcohol reduction. [name] (Co-Investigator) has written the Characters, Story and Narrative SMS for this intervention based on his Digital Narrative Transformation Framework to Health Behaviour Change. The underlying principles and structures for the practical use of commercial narrative engagement strategies and the embedding of BCTs and key messages in digital health behaviour change interventions is informed by his 20 years working in Film, Television and Computer Games as a screenwriter, producer and developer. This practice based approach was formalised in his subsequent PhD research (based on that expertise) entitled 'The Power of Digital Storytelling to Influence Human Behaviour'28. [name] and [name] conducted systematic reviews of quantitative, qualitative and economic evidence for the management of obesity in men. [name] conducted a review of incentives for weight loss which [name] is currently updating. [name] and [name] conducted systematic reviews and a mixed method study investigating the mechanisms of action of incentives for behaviour change to inform a DCE which showed promise for combining incentives with SMS for smoking cessation in pregnancy.

## 3. RESEARCH AIM AND OBJECTIVES

**Overall aim:** To co-produce with PPI, an acceptable and feasible RCT design with broad reach to test a narrative theory-based SMS intervention with embedded BCTs, with and without an endowment incentive, compared to waiting list control, to inform a future full trial.

**Phase 1.** This phase has finalised the design of the narrative SMS intervention, the incentive intervention and the trial design through mixed methods research and PPI. This phase received ethics committee approval from The University of Stirling on 8th January 2016 and will be complete by 31st December 2016. The results of a survey conducted on our behalf by IPSOS Mori with 1045 obese men, PPI and qualitative data support the protocol described below. £400 is consistent with existing evidence on the amount required to change behaviour, is equivalent to 12 months of the weight loss drug Orlistat alone (excluding the costs of health service staff time and monitoring); is similar to the costs of attending

commercial weight loss groups for a year. PPI are supportive of the incentive intervention which can be seen as presenting an opportunity for "harder to reach" men to improve their health and wellbeing.

## Phase 2. A feasibility trial to refine approach, recruitment, randomisation, intervention delivery, engagement, retention and follow-up processes.

## **Objectives:**

- 1. To assess the acceptability and willingness of obese men to be randomised to i) SMS ii) SMS and endowment incentive or iii) waiting list for SMS
- 2. To assess the acceptability and feasibility of recruiting obese men from GP practice obesity registers and community venues (identified in Phase 1 of this study).
- 3. To determine the acceptability of intervention content, delivery and attendance levels for objective weight measures at baseline, 3, 6, and 12 months and any unintended consequences
- 4. To assess the likely impact on % weight loss at 12 months and health inequalities via assessment of differential uptake and potential effectiveness by socio-economic group

## Progression criteria for a full trial

Progression criteria are based on systematic review evidence and ongoing NIHR studies. The findings of this study may or may not support a full trial, either two arm or three arm. The progression criteria are:

- Acceptability of the intervention and the control group (by the majority of the target group);
   willingness to be randomised. Evidenced by quantitative and qualitative data on:
   satisfaction, recruitment, intervention engagement
- 2. Feasibility of recruiting 105 men in 4 months
- 3. 12 month outcomes on at least 72 % of men randomised per group, consistent with a recent UK weight management trial in men and systematic reviews of male obesity literature
- 4. Evidence of mean weight loss of at least 3% of baseline weight at 12 months in any intervention group; 3% is defined by NICE as clinically significant
- 5. Independent SSC will decide whether the findings support a two or three arm trial or not
- 6. Commitment by e.g. government or NHS/local authorities to fund the incentive intervention, if it shows positive indicative effects, to ensure translation and sustainability

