WHAT-Procedures: The endowment incentive specification for weight loss targets (Box1) is informed by our updated systematic review of incentives for weight loss; loss aversion theory; preferences of 1045 obese men in the Phase 1 survey/DCE, a stakeholder workshop and PPI. Our weight loss targets are more ambitious than the typical 3% mean weight loss in weight management programmes quoted in NICE5, current systematic review evidence for obese men and the 5% weight loss at 12 months in the FFIT trial. The full sum of money can be secured or lost over the year depending on whether targets for weight lost since the start of the study are met: 5% of body weight lost at 3 months (£50 secured/lost), 10% at 6 months (£150 secured) and 10% at 12 months (£200 secured). At 6 and 12 months men lose some of the money for each % weight loss not attained between 5-10%. For weight loss below 5% since the start of the study, men lose all the money for that time point (see Table 1 below for details). Men will receive the money at 12 months based on the targets they met. Their weight at 12 months must be less than at baseline in order to receive any money, regardless of whether they have met interim weight loss targets. If men do not attend the 12 month assessment, they will not receive any money. The incentive will be triggered by researcher verified weight loss data at the baseline. 3, 6 and 12 month assessments (Blue Tooth Scales linked to the centralised database at University of Dundee with paper back-up copy). Feedback to men will be by text initially and will then be visible via the website.

Table 1. Incentive strategy contingent on meeting weight loss targets over 1 year

3 months: £50 - target 5%

	Money secured	Money lost
<5%	£0	£50
≥5%	£50	£0

6 months: £150 - target 10%

	Money secured	Money lost	
<5%	£0	£150	
5%	£75	£75	
6%	£90	£60	
7%	£105	£45	
8%	£120	£30	
9%	£135	£15	
≥10%	£150	£0	

12 months: £200 - target 10%

	Money secured	Money lost
<5%	£0	£200
5%	£100	£100
6%	£120	£80
7%	£140	£65
8%	£160	£40
9%	£180	£20
≥10%	£200	£0

**WHO PROVIDES**: Incentives are provided as part of this research grant and are triggered by researcher weight goal verification. Feedback on weight achievement and incentive status will be through SMS and a study webpage.

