## 4.5. OUTCOME MEASURES

**Primary outcome:** A decision whether to proceed to a full effectiveness and cost-effectiveness RCT for the SMS intervention, with or without an incentive, compared to a waiting list control. This will be based on the progression criteria set out in Section 3. Criteria include quantitative and qualitative outcomes for:

- Acceptability of the interventions and the control group (willingness to be randomised, intervention engagement, participant retention, qualitative views)
- Feasibility of recruiting 105 obese men across socioeconomic and cultural spectra, intervention delivery, outcome measures at each time point, the potential for assessor blinding
- Evidence of positive indicative weight loss effects at 12 months for at least one group
- Feasibility of gaining consent for longer term follow up and NHS data linkage

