## 4.9. SAMPLE SIZE

Feasibility RCT: We aim to randomise 105 men, 35 to each arm, in line with recent recommendations for pilot trials as sufficient to estimate key parameters for a full trial. We will conduct 18-30 face to face or telephone interviews (6-8 men from each trial group) recruited throughout the trial. This sample size is based on previous experience of conducting feasibility studies like this. A sampling frame will ensure diversity for socio-demographic and personal weight loss histories.

Mixed methods process evaluation: All men (n=105) who attend the 12 month assessment will be asked an open question for any suggestions for improving the study. Men who do not attend will be sent a final "thank you" letter informing them of how they can access the findings, and will be invited to provide feedback. Based on previous research experience of applying qualitative research in feasibility RCTs, 18-30 qualitative semi-structured interviews, with a diverse and information rich sample (6-10 from each trial group) are likely to be required to reach data saturation for key themes and for no new thematic issues to arise in interviews. However, some flexibility in the precise sample size is required, as it is impossible to predict important research questions that might arise in a complex intervention study like this. The PhD student will also conduct an additional 18-30 semi-structured interviews to investigate variation in engagement of men and to find out about their experiences after the intervention has finished.

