## 4.10. THE ANALYSIS PLAN FOR THIS STUDY

Given the feasibility nature of the study, the data reported will mainly be descriptive. Summaries of quantitative outcome measures (all time points) will be tabulated by intervention group, including means and standard deviations for continuous variables e.g. weight loss (or medians and interquartile ranges if data are skewed), and proportions for any dichotomous or categorical data. The proportion of individuals contacted who were recruited and the proportion retained in the study at various time-points by group will be determined. Unadjusted mean differences and risk ratios will be calculated for 12 month outcomes to determine evidence of

potential effect of the interventions to test progression criteria, but no further estimates of effect size will be modelled. Completion rates will be reported so that the feasibility of each outcome measure can be assessed. A sample size calculation for a full trial will be performed, incorporating the standard deviation and response rates for the primary outcome. The proportions of participants who ask to stop the texts, withdraw from the study and attend the 3 month assessments will be compared for the original and alternative text messages.

Health Economics: The feasibility of measuring cost and outcomes for the cost-effectiveness analysis in the full trial will be explored. In a future full trial, cost-effectiveness of the interventions will be measured as a cost per Quality Adjusted Life Year (QALY) from an NHS perspective. The resources associated with the interventions will be abstracted from study forms. Other NHS resource use will be collected from participant questionnaires. Resource use estimates will be combined with unit costs obtained from standard sources or study specific estimates. QALYs will be derived from the responses to the EQ-5D. The incremental cost effectiveness ratio (ICER) will be estimated by dividing the difference in mean total costs between the intervention and control group by the difference in QALYs. Bootstrapping will be used to estimate variability in the ICER. A Value of Information analysis will be done to give an indication of the optimal sample size of a future trial.

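### Progression criterion 4 is a within-arm, either-arm 3% threshold that never uses the waiting list, and it does not match the between-group analysis said to test it

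*Protocol*

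**What the plan says.** In the Protocol, Section 3 (Progression criteria for a full trial), criterion 4 reads "Evidence of mean weight loss of at least 3% of baseline weight at 12 months in any intervention group". It names no comparator. Criterion 3 asks for "12 month outcomes on at least 72 % of men randomised per group", criterion 5 leaves the choice between a two-arm trial, a three-arm trial or no trial to the independent Study Steering Committee (SSC), and criterion 6 concerns funding for the incentive.

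Section 4.5 makes the progression decision the study's primary outcome and restates the weight criterion as "Evidence of positive indicative weight loss effects at 12 months for at least one group", without a threshold or a comparator.

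Section 4.10 says "Unadjusted mean differences and risk ratios will be calculated for 12 month outcomes", the purpose being to look for "potential effect of the interventions to test progression criteria, but no further estimates of effect size will be modelled". The same section plans means by group at every time point.

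On size, Section 4.9 says "We aim to randomise 105 men, 35 to each arm". It justifies this number by published guidance on the size of pilot trials and gives no SD, effect size, alpha or power.

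In Section 4.3 (Intervention 2), payment in the incentive arm depends on the last visit: "If men do not attend the 12 month assessment, they will not receive any money".

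**The concern.** Three sections bear on one decision and describe it differently. Section 3 sets a within-arm change with a number. Section 4.5 asks for an indicative effect without a number. Section 4.10 plans between-group estimates that correspond to no written criterion. What would evaluate criterion 4 as worded is the table of means by group, not the mean differences.

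The study randomises to a waiting list, and Section 4.5 proposes the between-group difference at 12 months as the full trial's primary outcome. Criterion 4 sets that information aside. Weight loss without any effect of the interventions is possible here: men join in order to lose weight, all receive NHS weight-loss information and a pedometer, and control men may try to lose weight as they choose. Section 4.3 itself describes 3% as the usual mean loss in weight management programmes. The threshold also has two chances to be met, and the text does not say what a pass in one arm means for the other.

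At stake is whether the weight evidence put to the SSC answers the question that randomisation was meant to inform.

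**Working it through.** **The plan's own figure.** 3 arms × 35 = 105, as stated. The protocol gives no error rate or power for criterion 4, so there is nothing else to reproduce.

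**Inputs.**
- Threshold of 3% in either of two intervention arms (Section 3, criterion 4).
- 35 men per arm (Section 4.9).
- Lowest retention allowed by criterion 3: 0.72 × 35 = 25.2, so 26 men weighed per arm.
- SD of percentage weight change at 12 months: not stated. Assumed 5 to 8 points.
- The same true mean loss μ in all three arms, so no benefit over the waiting list.

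**Formulas (normal approximation).** One named arm: p = 1 − Φ((3 − μ)/(SD/√26)). At least one of two independent arms: 1 − (1 − p)².

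**Worked case.** With SD 6 and μ = 2, the standard error is 6/√26 = 1.18. Then (3 − 2)/1.18 = 0.85, p = 0.198, and either arm passes with probability 1 − (1 − 0.198)² ≈ 0.36.

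| True loss shared by all arms | One named arm ≥3% | At least one arm ≥3% |
|---|---|---|
| 0% | 0.1-2.8% | 0.2-5.5% |
| 1% | 2-10% | 4-19% |
| 2% | 15-26% | 28-46% |
| 3% | 50% | 75% |

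Ranges run from SD 5 to SD 8. With all 35 men weighed per arm, the either-arm figure at a shared 2% is 22-41%.

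**Adding a control comparison.** Keep the 3% threshold and also require a point estimate better than control (simulation, three arms sharing one control, 26 men each). The either-arm pass probability becomes:
- shared 2%: 26-40%, against 28-46%;
- shared 3%: 58%, against 75%;
- true 3% in both intervention arms and 0% in control: 74.5-75%, against 75%.

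**Precision of one arm against control.** The 95% CI half-width is 1.96 × SD × √(2/26): 2.7 points at SD 5 and 4.4 (4.35) at SD 8.

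**Missing weights.** If only attendees entered the mean and the other 9 of 35 men lost nothing, a 3% attendee mean would be (26/35) × 3 = 2.2% over all randomised men. A 3% mean over all randomised would need attendees to average 3 × 35/26 = 4.0%.

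**The case against.** The best defence is that criterion 4 does not act alone. It is one of six, the protocol says the findings may or may not support a full trial, and the independent SSC decides with the unadjusted comparisons from Section 4.10 available to it. Section 4.5 speaks of indicative effects, which can be read as including the control comparison. This stands against one tempting inference, that an ineffective intervention would by itself set off a full trial: meeting criterion 4 is not sufficient. It does not remove the mismatch, because no written criterion asks for an advantage over control.

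A reader might also infer that the 3% mean is an attendees-only mean. The documents do not say so. The analysis set and the handling of missing weights may be settled in a statistical analysis plan that is not at hand, so their absence is no finding. A firm claim that the incentive arm's mean will be inflated is likewise unsupported. Payment does depend on attending, but all men are offered £20 for the 12-month visit, non-attenders get two reminders and another appointment, and home visits are possible. Any figure for such bias needs an invented association between attendance and weight.

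The either-arm form is partly deliberate, since a two-arm full trial is allowed and the research questions ask about one or both interventions. Nothing says that a pass in one arm carries the other.

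Finally, the pass probabilities depend on how much weight untreated men lose. Near 0% the rule is rarely met by chance, and the documents do not show that the waiting list will lose 2% or more.

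**Conclusion.** The point holds as a defect of the decision rule: the threshold is within-arm, met by either arm and uncontrolled, and Sections 3, 4.5 and 4.10 do not describe the same test. With no benefit over control, its consequence runs from negligible (0.2-5.5% at a shared 0% loss) to large (75% at a shared 3%). These figures rest on an assumed SD of 5 to 8 points, 26 men per arm and a normal approximation. The spread is itself the argument, because control-arm change determines the answer and the rule ignores it. This is a go/no-go rule in a mainly descriptive feasibility study, so the figures should not be read as the type I error of a confirmatory test. Severity: should-fix.

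**What to change.** Reconcile Sections 3, 4.5 and 4.10. Restate criterion 4 for each intervention arm separately, as both of the following:
- a mean loss of at least 3% of baseline weight at 12 months; and
- an intervention-minus-control difference in percentage weight loss at 12 months whose point estimate favours the intervention, given to the SSC with its 95% CI and with no significance requirement.

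Beside it, show a sensitivity mean over all randomised men, for example with missing weights set to baseline, because payment in the incentive arm depends on the 12-month visit. Do not make that mean the gate. With 26 of 35 men attending at random, a true 3% loss and 0% in control, gating on it would cut the per-arm pass probability from 50% to 15-25%.

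The cost is wording only, since the data and estimates are already planned. The criterion becomes slightly harder to meet, with almost no loss when the effect is real. The gain is also modest: false passes fall from 28-46% to 26-40% at a shared 2% loss and from 75% to 58% at a shared 3%. The difference will be imprecise at this size, so its main value is that the SSC sees it, with its interval, as part of the written rule.
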